11.1.4 Safety set

The Safety set (SAF) is defined like the FAS.

11.1.5 PD analysis set

The PD analysis set (PDS) includes all subjects who received at least 4 weeks of study treatment and have an absolute lymphocyte count measurement at baseline and at least one measurement between the Week 4 visit and Week 12 visit.

11.1.6 PK analysis set

The PK analysis set (PKS) includes all subjects from the SAF, who provided at least one blood sample.

11.1.7 Extension set

The extension set (ES) includes all subjects enrolled in the Extension Treatment Period who received at least one dose of ponesimod in the Extension Treatment Period.

11.1.8 Usage of the analysis sets

The primary analysis is based on the PD variable and will be performed on the PDS (main analysis) and on the FAS as well. Sensitivity analyses of the primary analysis will be performed based on the PDS and FAS.

All Safety variables will be analyzed using the SAF.

Exploratory efficacy variables will be analyzed using both FAS and PPS, as applicable. Details will be provided in the SAP.

Quality of Life endpoints will be analyzed based on the FAS.

PK evaluations will be analyzed using the PKS, and PD evaluations (other than primary PD variable) will be analyzed based on the PDS.

All safety and efficacy endpoints in the Extension Treatment Period will be analyzed on the ES.

11.2 Variables

11.2.1 Primary PD variable

The change in absolute lymphocyte count from baseline to Week 4, Week 8 and Week 12 in the Core Treatment Period is defined as:

- l_d = Absolute lymphocyte count for dose d – absolute lymphocyte count at baseline

The change in absolute lymphocyte counts (l_d) is assessed at Week 4 for the 5 mg dose, at Week 8 for 10 mg and at Week 12 for 20 mg in the Core Treatment Period.

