11 STATISTICAL METHODS

All statistical analyses will be conducted by Actelion or by designated contract research organizations supervised by Actelion.

The Statistical Analysis Plan (SAP) will be approved prior to database lock for the final analyses. The SAP provides the full details of all analyses, data displays, and algorithms to be used for data derivations.

All data will be listed, and endpoints will be summarized by appropriate descriptive statistics (tables or figures), typically including:

- Number of non-missing observations, number of missing observations, mean, standard deviation (STD), median, Q1, Q3, minimum and maximum for continuous endpoints;
- Number of non-missing observations, number of missing observations and frequency with percentage per category (percentages based on the number of non-missing observations) for categorical endpoints;
- Number of subjects at risk, cumulative number of events, cumulative number of censored observations and Kaplan-Meier estimates of the survival function for time-to-event endpoints.

Absolute changes from baseline are defined as: post-baseline value minus baseline value, i.e., a positive sign indicates an increase as compared to baseline.

A percentage (relative) change from baseline is defined as the absolute change from baseline divided by the baseline value (if the baseline value not equal 0) multiplied by 100.

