11.2.6 Overall testing strategy of the PD variable

The primary analysis of this study is based on the absolute lymphocyte counts at pre-specified time points. Hypotheses are setup to establish a within-subject dose response at baseline vs the Week 4 (5 mg), Week 8 (10 mg) and Week 12 (20 mg) assessments in the Core Treatment Period.

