11.2.7.2 Handling of missing data

As the PDS includes all subjects who received at least 4 weeks of study treatment with at least one valid lymphocyte measurement on or after the Week 4 assessment, all available data at the visits of interest (Week 4, Week 8 and Week 12) will be included in the analysis. Thus, data of subjects with one, two or three post-baseline measurements at the predefined time points will contribute to the dose-response analysis. Every effort will be made to collect lymphocyte data, as complete as possible, for every subject at every visit. Last observation carried forward (LOCF) will be used as a sensitivity analysis as described below.

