11.2.7.3 Main analysis of the primary PD variable (primary analysis)

To meet the objective of demonstrating existence of an intra-subject dose response on the absolute lymphocyte count reduction from baseline in subjects with GVHD, at least one null hypothesis must be rejected with a one-sided significance level of 5%. The type-1 error will be controlled via a hierarchical ordering of the tests: pairwise comparisons will be conducted in decreasing dose order. Within-subject t-tests will be performed at each dose level (assuming normally distributed data).

In addition, an E_{\max} model will be fitted for the baseline, Week 4, Week 8 and Week 12 data. The data will be summarized with point-wise and model-based estimates, standard deviation and 95% CIs on the reduction in absolute lymphocyte counts from baseline at the examined dose levels. A plot of the estimated dose-response curve with 95% credibility interval limits will be presented along with the observed response at each dose.

The primary analysis will be performed on the PD analysis set and conducted after the last patient has completed the Follow-Up 1 visit in the Core Treatment Period.

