11.2.7.4 Supportive/sensitivity analyses

A sensitivity analysis of the primary analysis will be performed on the FAS (in case the FAS does not contain the same number of subjects as the PDS).

Further t-tests will be performed across dose levels (5 mg vs 10 mg, 5 mg vs 20 mg and 10 mg vs 20 mg). These tests, performed at a one-sided significance level of 5%, will be

considered as exploratory. These pairwise comparisons will be performed on the FAS and PDS.

An LOCF approach (using the Week 4 visit or later) will be performed for subjects with a missing Week 8 or Week 12 assessment, based on the FAS.

The dose-response modeling will be repeated using the Week 4, Week 8 and Week 24 assessment (instead of the Week 12 assessment), based on the PDS.

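### The dose-response analysis assigns dose by visit, so its estimates describe the scheduled regimen and not the dose taken; the LOCF sensitivity analysis mixes doses by its own rule (minor, cheap to improve)

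*Combined protocol and SAP*

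**What the plan says.** Section 11.2.1 defines the primary variable from the "Absolute lymphocyte count for dose d" minus the baseline count, and then ties each dose to one visit: the change "is assessed at Week 4 for the 5 mg dose, at Week 8 for 10 mg and at Week 12 for 20 mg". Section 11.2.6 repeats the pairing, describing a "within-subject dose response at baseline vs the Week 4 (5 mg), Week 8 (10 mg) and Week 12 (20 mg) assessments".

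The main analysis uses the PD analysis set. Its definition (11.1.5) asks for 4 weeks of treatment, a baseline count and one count between Weeks 4 and 12, with no condition on dose. Section 11.2.7.2 adds that "all available data at the visits of interest (Week 4, Week 8 and Week 12) will be included in the analysis". Section 11.2.7.3 asks for within-subject t-tests at each dose level and an Emax "model will be fitted for the baseline, Week 4, Week 8 and Week 12 data", with estimates and 95% CIs at the examined doses.

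Two supportive analyses in 11.2.7.4 matter here. On the full analysis set, "An LOCF approach (using the Week 4 visit or later) will be performed for subjects with a missing Week 8 or Week 12 assessment". On the PD analysis set, "The dose-response modeling will be repeated using the Week 4, Week 8 and Week 24 assessment", with Week 24 in place of Week 12.

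Section 11 leaves the detail elsewhere: "The SAP provides the full details of all analyses, data displays, and algorithms to be used for data derivations". That document was not available, so this point covers the protocol text only.

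**The concern.** Being on the scheduled dose at the scheduled visit is not guaranteed, even for a subject who follows the protocol exactly. By Week 12 a compliant subject can be on a lower or re-titrating dose through any of these routes:

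- escalation not permitted at Day 29 or Day 57 (5.1.2.3);
- a spirometry result that stops further escalation (5.1.10.7);
- an interruption of 4 or more doses starting on Days 2-56, after which escalation is barred (5.1.8, Scenario 2);
- an interruption that includes Day 57, after which 10 mg is restarted and 20 mg delayed (Scenario 3, exception ii);
- re-titration after 4 or more missed doses from Day 57 on (Scenario 4);
- a confirmed lymphocyte count below 0.1 × 10^9/L at Week 8 that leads to a dose reduction (5.1.10.2).

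Reductions from 20 mg for low counts, and liver-test interruptions (5.1.10.3), bear mainly on the Week 24 refit. Section 5.1 itself expects last tolerated doses of 5, 10 or 20 mg.

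The first main objective is the dose response in lymphocyte reduction, and the monitoring committee is to recommend a dose for development (3.5.1). An estimate read as the 20 mg effect should not, without saying so, include counts taken on 5 or 10 mg.

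**Working it through.** **Inputs.** Plan means (SD), × 10^9/L, from 11.4.2: baseline 1.20 (0.60), 5 mg 0.85 (0.40), 10 mg 0.60 (0.35), 20 mg 0.40 (0.25). N = 30, with 23 reaching Week 12 in the dropout case (11.4.1). One-sided alpha 0.05. The documents give no share of subjects off the scheduled dose and no within-subject correlation. I assume shares as stated below and correlations of 0.3 and 0.5.

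**1. The plan's own figure.** Power for 5 mg against baseline = Φ(0.35/√((0.6² + 0.4²)/n) − 1.645). For n = 30 this is Φ(2.658 − 1.645) = 84.5%. For n = 23 it is Φ(2.328 − 1.645) = 75.3%. The plan states about 85% and 75%, so the inputs are read as the plan uses them.

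**2. Off-dose subjects in the by-visit Week 12 mean.** With share f held at a lower dose, the mean is (1 − f) × 0.40 + f × (mean at the lower dose).

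| Assumed 10% of subjects | Week 12 mean | Change from 1.20 |
|---|---|---|
| none off dose | 0.400 | -0.800 |
| held on 10 mg | 0.9 × 0.40 + 0.1 × 0.60 = 0.420 | -0.780 |
| held on 5 mg | 0.9 × 0.40 + 0.1 × 0.85 = 0.445 | -0.755 |
| strong responders, count 0.20 | 0.9 × 0.40 + 0.1 × 0.20 = 0.380 | -0.820 |

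The last row shows that the shift can go either way.

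**3. Against sampling error.** SE = √(0.6² + 0.25² − 2ρ × 0.6 × 0.25)/√30, which is 0.105 at ρ = 0.3 and 0.095 at ρ = 0.5. Every shift in step 2 (0.02 to 0.045) is less than half an SE. A shift of one SE needs SE/0.45 = 21-23% of subjects on 5 mg, or SE/0.20 = 48-53% on 10 mg.

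**4. Tests (20,000 simulated trials, held subjects given the 5 mg mean and SD at Weeks 8 and 12).** Week 12 against baseline keeps power 1.00 with 15 of 30 held. The exploratory 20 against 10 mg test falls from 0.90 to about 0.81 (3 of 30 held) and 0.62 (8 of 30) at ρ = 0.3. At ρ = 0.5 it falls from 0.96 to 0.90 and 0.73.

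**5. LOCF.** The dropout case leaves 30 − 23 = 7 subjects to fill.
- All from Week 4: (23 × 0.40 + 7 × 0.85)/30 = 0.505, change -0.695. A nominal 95% CI covers -0.80 in about 87% (ρ = 0.3) or 85% (ρ = 0.5) of simulated trials.
- All from Week 8: (23 × 0.40 + 7 × 0.60)/30 = 0.447, change -0.753. Coverage is about 93%.
- Week 8 cell filled from Week 4: (23 × 0.60 + 7 × 0.85)/30 = 0.658, change -0.542 instead of -0.60.

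**6. Time on dose in compliant samples.** The PD marker is measured with the hematology tests (7.2.2). Blood may be drawn up to 3 days before the Week 4 and Week 8 visits and up to 7 days before or after the Week 12 visit (8.2.2 to 8.2.4), on top of visit windows of ±3, ±3 and ±7 days. The shortest compliant times are:
- 5 mg: visit on Day 26, draw on Day 23, so Days 7-22 = 16 days.
- 10 mg: late Week 4 visit (Day 32), 10 mg from Day 36; Week 8 visit on Day 54, draw on Day 51, so Days 36-50 = 15 days.
- 20 mg: late Week 8 visit (Day 60); Week 12 visit on Day 78, draw on Day 71, so Days 60-70 = 11 days.

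For comparison, the earliest Scenario 4 restart (Day 61) towards 20 mg reaches it on Day 75. That gives 10 days on dose before a Day 85 sample.

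**The case against.** The strongest reply is that a rule is stated. Sections 11.2.1, 11.2.6 and 11.2.7.2 together describe a by-visit analysis of all available counts. That is a legitimate scheduled-regimen analysis, and I would keep it. Handling of dose at visit is also the kind of derivation that section 11 assigns to the SAP. Both parts stand. What remains is that 11.2.1 speaks of the count for a dose while the analysis conditions on the visit, and nothing in the protocol text tells the reader which quantity is being estimated.

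Second, the amounts are small. Shares are assumed, 10% shifts are inside sampling error, and the tests that lose power are declared exploratory. This stands too, and it sets the weight.

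Third, LOCF is only a sensitivity analysis, and the worst case needs all 7 subjects to leave after a Week 4 count and before Week 8. Anyone leaving before Week 4 has nothing to carry. So -0.695 is an upper limit on the distortion under the plan's dropout case. The mixing itself needs no assumption about dose holds, because it follows from the rule as written.

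A reader might infer that the 20 mg effect must be understated. The documents do not support that: if strong responders are the ones kept on a lower dose, the by-visit mean can be larger than among subjects who reach 20 mg. A reader might also infer that the plan labels Week 24 as 20 mg. It does so only by implication, by putting Week 24 in the place of Week 12.

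**Conclusion.** The point holds as a minor one. The by-visit means, Emax curve and exploratory between-dose tests estimate the effect of the scheduled regimen, and the text should say so. The LOCF analysis enters counts at the wrong dose. With 7 of 30 filled, the Week 12 change moves from -0.80 to between -0.753 (all from Week 8) and -0.695 (all from Week 4), with CI coverage of about 93% and 85-87%.

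It would be tempting to conclude that the primary result is at risk. It is not: the any-dose test against baseline keeps essentially full power, and the main PD-set analysis imputes nothing, so the LOCF distortion does not reach it. Off-dose subjects can enter the main by-visit means, but at an assumed 10% they move the Week 12 mean by 0.045 at most when held on 5 mg, against an SE of 0.095-0.105.

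These sizes rest on the plan's means and SDs, correlations of 0.3 to 0.5, and held subjects having average counts for their dose. The true off-dose share is unknown from the documents, and the SAP may already settle the matter.

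**What to change.** 1. Keep the by-visit analysis and call it the scheduled-dose estimate in 11.2.1.
2. Add a pre-specified sensitivity analysis of mean changes, between-dose comparisons and the Emax fit (including the Week 24 refit), indexed by the dose actually taken according to the study drug log and eCRF. Tabulate actual dose by visit at Weeks 4, 8, 12 and 24.
3. In that analysis, set aside off-drug and re-titrating samples. Use a minimum time on dose justified from the time-to-effect data cited in 3.3 and checked against the draw windows. Compliant samples can have as few as 16, 15 and 11 days on 5, 10 and 20 mg, so a 14-day minimum, for instance, would drop some compliant 20 mg samples. Define off-drug so that it allows for the EOT1 draw, which 8.2.6 places 1 to 3 days after the last dose.
4. Replace LOCF across dose levels with an analysis that keeps each count at the dose at which it was measured, for example a repeated-measures or Emax model on available data.
5. If the SAP already contains such rules, a cross-reference in 11.2.1 is enough.

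The cost is SAP wording and programming. Last administration before each visit (5.1.2.2) and dose adjustments and interruptions (5.1.6) are already recorded in the eCRF, and no visit or dosing rule changes. The drawback is that actual-dose groups are selected by tolerability and response, so both analyses should be shown side by side.

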11.2.2 Safety variables

The following safety endpoints/variables will be analyzed. The SAP will summarize these analyses in more detail. Safety endpoints will be analyzed from first study drug intake up to 30 days (inclusive) after last study drug intake.

Overall safety endpoints

- Treatment-emergent AEs, SAEs, and AEs of special interest
- AEs leading to premature discontinuation of study drug
- Deaths

Absolute lymphocyte count

- Treatment-emergent absolute lymphocyte count $< 0.2 \times 10^9/L$ ($< 200 \text{ cells/mm}^3$)

Cardiac rate and rhythm safety endpoints

- Treatment-emergent morphological ECG abnormalities
- Change in 12-lead ECG variables (HR, PR, QRS, QT, QTcB, QTcF) from pre-dose to selected post-dose assessments (1h, 2h, 3h, 4h) on Day 1 and on day(s) of re-initiation of study drug
- Notable abnormalities for selected 12-lead ECG variables (HR, PR, QT, QTc) at 3 h post-dose assessment on Day 1 and pre-dose on Weeks 4, 8, 12, and 24 (notable abnormalities definition in Appendix 6)
- Cardiac safety events will include:
 - Treatment-emergent QTc $> 450 \text{ ms}$ (male), $> 470 \text{ ms}$ (female), $> 500 \text{ ms}$ (male), and $> 520 \text{ ms}$ (female)
 - Treatment-emergent QTc increase from baseline $> 30 \text{ ms}$, $> 60 \text{ ms}$
 - Other treatment-emergent abnormalities observed by 12-lead ECG
 - Treatment-emergent (serious) cardiac AEs of special interest.

Confidential

Pulmonary function safety endpoints

- Treatment-emergent decrease of FEV₁ or FVC > 20% from baseline values
- Treatment-emergent decrease of percent of predicted FEV₁ or FVC > 20% from baseline values
- Change in FEV₁ and FVC from baseline, absolute and % of absolute change to all visits up to FU1
- Among subjects with a decrease of > 200 mL and > 12% in FEV₁ or FVC, respectively, from baseline to EOT1, reversibility defined as a decrease of < 200 mL and < 12% in FEV₁ or FVC, respectively, from baseline to last available follow-up
- Change from baseline to FU1 vs change from baseline to EOT1, in FEV₁ or FVC (absolute and % of predicted)
- Change in lung diffusion capacity as assessed by DL_{CO} expressed in absolute change and % of predicted value from baseline to all time points up to FU1
- Change from baseline to FU1 vs change from baseline to EOT1 in DL_{CO} (absolute and % of predicted)
- (Serious) pulmonary AEs of special interest
- Withdrawal due to pulmonary reasons/AE

Other safety endpoints

- Treatment-emergent notable BP abnormalities [definition in Appendix 6].
- Treatment-emergent notable laboratory abnormalities [definition in Appendix 6].

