	Hematology**/Chemistry**/ Urinalysis	X	X pre-dose	X (4) pre-dose /local and central lab	X pre-dose
	Tuberculosis test**	X			
	Viral serology**	X			
	Additional blood samples for exploratory biomarkers**		X		
	Pregnancy test**/ MOC* (5)	X serum**	X serum/urine*	X urine*	X urine*
	PK and PD** sampling		X See Section 7.2.1	X pre-dose	X pre-dose & 3 hr post-dose
	Study drug dispensing & accountability (6)**		X	X	X
	AEs & SAEs (7)*	X	X	X	X

*Data collected in the eCRF **Electronically transferred to the sponsor

Table 1 Visit and assessment schedule (continued)

Periods	Name	Continued: CORE TREATMENT PERIOD, COURSE 3 (20 mg)			UNSCHEDULED Applies to all periods in Table 1	FOLLOW-UP PERIOD 1	
		16 Weeks					
Visits	Number	6	7	8	R1, R2, ...	U1, U2, ...	9, 10
	Name	W16	W20	W24 (EOT1)	Re-initiation	Un-scheduled	FU1, FU2 (8)
	Time	Week 16	Week 20	Week 24 (earlier if prematurely discontinued)	Any day between Day 1 and EOT2	Any day between Day 1 and EOS	EOT1+30 & EOT1+90 days
	Visit window	± 7 days	± 7 days	± 7 days	NA	NA	+ 7 days
Chronic GVHD Activity Assessment, Form A and B*				X			X (9)
Lee Symptom Scale*				X			X (9)
Concomitant medications*		X	X	X	X	X	X
Physical examination*				X		Optional	
Body weight and height*				X (weight only)		Weight optional	
Systolic/diastolic blood pressure*		X pre-dose	X pre-dose	X	X See Section 5.1.7	X pre-dose	X (FU1 only)
12-lead ECG (2)**		X pre-dose	X pre-dose	X	X See Section 5.1.7	Optional; pre-dose	X (FU1 only)
Ophthalmological examination				X		Optional	
OCT (3)				X		Optional	
Spirometry*/DLco*				X		Optional	X (FU1 only)
Hematology**/Chemistry**/Urinalysis		X pre-dose	X pre-dose	X	X pre-dose	Optional	X
Additional blood samples for exploratory biomarkers**				X			X (FU1 only)
Pregnancy test*/MOC* (5)		X urine	X urine	X urine	X urine	Optional urine	X urine
PK and PD** sampling		X pre-dose	X pre-dose	X			X (PD only) (FU1 only)
Study drug dispensing & accountability (6)**		X	X	X	X		
AEs & SAEs (7)*		X	X	X	X	X	X

*Data collected in the eCRF **Electronically transferred to the sponsor

Table 1 Visit and assessment schedule (continued)

Periods	Name	EXTENSION TREATMENT PERIOD				FOLLOW-UP PERIOD 2
		Duration	96 Weeks			
Visits	Number	11	12, 13, 14, 15, 16	17, 18, 19, 20, 21, 22	23	24
	Name	EX-1 (8)	EX-2, 3, 4, 5, 6	EX-7, 8, 9, 10, 11, 12	EX-13	FU3 (EOS) (8)
	Time	EOT1 + 7 days to EOT1 + 90 days (10)	EX-Weeks 4, 8, 12, 16, 20	EX-Weeks 24, 36, 48, 60, 72, 84	EX-Week 96 (EOT2)	EOT2 + 30 days

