8.2.6 Visit 8 – EOT1 Visit

The EOT1 visit will take place at Week 24 (\pm 7 days) or earlier in case of premature discontinuation of study drug. In all cases, the EOT1 visit must take place 1 to 3 days after the last dose of study drug. It is strongly preferred that the EOT1 visit takes place 1 day after the last dose of study drug. Spirometry, DLco, hematology, blood chemistry, urinalysis and pregnancy tests should be performed 1 to 3 days after the last dose of study drug and do not need to be performed on the same day as the EOT1 visit. OCT and the

ophthalmological examination may be performed up to 7 days after the last dose of study drug.

The visit includes:

- Administer Chronic GVHD Activity Assessment – Patient self-report [Appendix 7 – Form B]
- Administer LSS (subject completes the questionnaire after patient self-report but prior to any clinical assessments or interaction with health care providers, preferably while waiting for their appointment)
- Chronic GVHD Activity Assessments - physician assessed [Appendix 7 – Form A]
- Recording of changes in concomitant medications
- Assessing and recording of MOC (for WOCBP only)
- SBP/DBP
- 12-lead ECG
- Body weight
- Physical examination
- Spirometry (under the responsibility of the pulmonologist)
- DLco (under the responsibility of the pulmonologist)
- OCT (under the responsibility of the ophthalmologist)
- Ophthalmological examination (under the responsibility of the ophthalmologist)
- Hematology, blood chemistry, PK/PD and exploratory biomarker assessments (blood lymphocyte subsets, plasma biomarkers, exploratory biomarker samples)
- Urinalysis
- Urine pregnancy test for WOCBP (if applicable)
- Recording of AEs and SAEs
- Study medication accountability and compliance review
- IRT call
- Remind WOCBP to use the MOC defined for this study. The reminders must be documented in the hospital chart.
- Schedule an appointment for next visit.

8.3 Core Safety Follow-up Period / Follow-up Period 1

The Follow-up Period 1 consists of the 30-day (+7 day window) post-core treatment safety follow-up visit (FU1) and the 90-day (+7 day window) post-core treatment safety follow-up visit (FU2).

The EOS visit occurs:

- At visit FU1 if a subject discontinues study drug prematurely during the Core Treatment Period.

Confidential

- At FU2 if the subject does not prematurely discontinue study drug during the Core Treatment Period.

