11.2.10 Analysis of the safety variable(s)

All safety analyses will be conducted on data up to 30 days (inclusive) after last study drug intake for the Core Treatment Period and for the Extension Treatment Period. All AEs will be coded using the latest version of MedDRA available at the time of database closure.

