11.2.10.1.3 Deaths

Fatal SAEs occurring any time after the start of treatment will be summarized in a similar manner as described above. Fatal SAEs will also be summarized for the Extension Treatment Period.

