11.2.10.4 Pulmonary safety

11.2.10.4.1 PFT

Descriptive summary statistics by visit will be provided for observed treatment-emergent values and changes from baseline by visit in FEV₁, FVC and FEV₁/FVC ratio (all expressed in absolute change, % change and % change of percent predicted value).

The number and proportions of treatment-emergent decreases of FEV₁ or FVC and percent predicted FEV₁ or FVC > 20% from baseline up to Week 24 will be summarized.

Reversibility of pulmonary parameters will be analyzed at the last available follow-up visit. The analysis will summarize subjects still showing a decrease of > 200 mL in FEV₁ and FVC or a change in FEV₁ and FVC of > 12% from baseline at the follow-up visit among subjects with a decrease of > 200 mL or > 12% in FEV₁ or FVC from baseline to EOT1.

The mean (and 95% CIs) change from baseline to FU1 and from baseline to EOT1 in FEV₁ or FVC (absolute and % predicted) will be summarized and plotted. A scatter plot will display the change from baseline to EOT1 versus the change from baseline to FU1 on an individual subject level.

PFT data will be analyzed in a similar manner during the Extension Treatment Period.

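### The 30-day post-dose cut is applied to all safety analyses, so FU1 lung-function data would be kept or dropped by scheduling, and non-fatal events on days 31–90 have no planned summary

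*Combined protocol and SAP*

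**What the plan says.** **The cut.** Section 11.2.2 opens the list of safety variables with "Safety endpoints will be analyzed from first study drug intake up to 30 days (inclusive) after last study drug intake". Section 11.2.10 says the same of both treatment periods: "All safety analyses will be conducted on data up to 30 days (inclusive) after last study drug intake". Sections 6.2 and 10.1.1 use 30 days more narrowly, to define what counts as treatment-emergent.

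**Endpoints at follow-up.** Below its 30-day sentence, Section 11.2.2 lists change in FEV1, FVC and DLco up to FU1, the FU1 change set against the EOT1 change, and reversibility at the last available follow-up. Section 11.2.10.4.1 adds: "Reversibility of pulmonary parameters will be analyzed at the last available follow-up visit". It also plans FU1 means with 95% confidence intervals and a subject-level scatter plot. Section 11.2.10.4.2 plans the FU1 versus EOT1 summary for DLco.

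**Timing of FU1.** Table 1 puts FU1 and FU2 at "EOT1+30 & EOT1+90 days", with a window of +7 days and none before. Section 8.3 repeats the +7-day window. Section 3.2.3 counts follow-up from the last dose and gives no window. On EOT1, Section 8.2.6 says "In all cases, the EOT1 visit must take place 1 to 3 days after the last dose of study drug", while Section 3.2.2 allows up to 7 days. Section 7.3.3 lets spirometry at FU1 be done 7 days either side of the visit date, and Section 7.3.4 ties DLco to spirometry.

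**Late events.** Sections 10.1.5.2 and 10.2.2.4 collect AEs and SAEs to day 90 from Core completers who do not enter the extension. Section 11.2.10.1.1 tabulates treatment-emergent events. Section 11.2.10.1.3 makes one exception: "Fatal SAEs occurring any time after the start of treatment will be summarized".

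**The concern.** A rule that defines treatment-emergent events has been widened to cover every safety endpoint, including measurements whose purpose is to show what happens after the drug is stopped. FU1 is scheduled at or just beyond the limit. Table 1 has no spirometry at FU2, so FU1 is the scheduled Core visit for judging recovery of lung function.

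Two things are at stake. First, a programmer who applies Sections 11.2.2 and 11.2.10 as written would retain one subject's FU1 lung test and discard another's because of the appointment date. With about 30 subjects, and reversibility assessed only in those with a defined decline at EOT1, a few exclusions could change the summary. Second, Amendment 2 lengthened the safety follow-up, but no planned summary of non-fatal events uses the added time.

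**Working it through.** The plan gives no figure of its own on this point. The check is a day count from the last dose (day 0), compared with a limit of day 30 inclusive.

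**Inputs**
- EOT1 lag after last dose: 1–3 days (Section 8.2.6), or up to 7 days (Section 3.2.2). The minimum is 1 day, since Section 5.1 ends dosing on the day before EOT1.
- FU1 at +30 days and FU2 at +90 days, each with a window of 0 to +7 days (Table 1, Section 8.3).
- Lung tests at FU1: visit date ±7 days (Sections 7.3.3 and 7.3.4).

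**Formulas**
- Visit day = lag + 30 (or 90) + window. The lag is 0 when the last dose is the anchor.
- Lung-test day = FU1 visit day ± 7.

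| Anchor | FU1 visit | FU1 days within cut | FU1 lung test | Lung-test days within cut |
|---|---|---|---|---|
| Last dose | 30 to 30+7 = 37 | day 30 only | 30−7 = 23 to 37+7 = 44 | 23–30 |
| EOT1, lag 1–3 | 1+30 = 31 to 3+30+7 = 40 | none | 31−7 = 24 to 40+7 = 47 | 24–30 |
| EOT1, lag up to 7 | 31 to 7+30+7 = 44 | none | 24 to 44+7 = 51 | 24–30 |

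The possible lung-test days inside the cut number 8 of 22, 7 of 24 and 7 of 28 in the three rows. These are counts of permitted calendar days. They do not estimate the proportion of subjects, which depends on how sites book the tests.

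**FU2** falls on days 90–97 from the last dose, or 1+90 = 91 to 7+90+7 = 104 from EOT1. It is always outside the cut.

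**FU3** has the same problem. It falls on days 30–37 from the last dose (Section 8.4.5), or 31–40 from EOT2 with a 1–3 day lag (Table 1).

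**Late events.** For Core completers not entering the extension, 90 − 30 = 60 of the 90 collection days lie beyond the cut. Section 11 plans a summary of fatal SAEs for those days and none for other AEs or SAEs.

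**Search for an exemption.** None appears in Sections 11.2.2, 11.2.10, 11.2.10.4.1 or 11.2.10.4.2. The last two describe the by-visit summaries as covering treatment-emergent values, which under Section 6.2 again points to day 30.

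**The case against.** The strongest reply is that the specific governs the general. Section 11.2.2 names the FU1 endpoints right after the 30-day sentence, and Section 11.2.10.4.1 specifies FU1 outputs in detail, so the sponsor plainly means to analyse them. That stands as evidence of intent. A reader might infer that the plan sets out to drop FU1, and the documents do not support this. They show a missing exemption clause.

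A reader might also infer that the rule leaves no lung data for reversibility, or only visits on exactly day 30. That is wrong too: the 7-day allowance before the visit puts some tests inside the cut. Section 5.1.10.7 also requires spirometry 7–10 days after discontinuation in subjects who fail the bronchodilator challenge.

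Further points in the plan's favour:
- Lymphocyte reversibility from EOT1 to FU1 is planned as a PD analysis (Section 11.2.11.3), outside the safety cut, although Section 11.2.10.6.2 also lists it as a laboratory safety event.
- A 30-day treatment-emergent period is generous. With a half-life of about 32 h, 30 × 24 / 32 = 22.5 half-lives.
- Later events may reflect the standard of care started after EOT1. They are still listed (Section 11), SAEs are still reported, and deaths are summarised.
- Section 11 defers detail to an SAP, which could hold a visit-windowing rule.

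These points lower the importance but do not remove the conflict. Two sections state the cut for all safety analyses, nothing in the available text lifts it, and a listing is not a summary.

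**Conclusion.** The point holds as a conflict between a general rule and named endpoints. Under Table 1 the FU1 visit is never within 30 days of the last dose (days 31–40, or to day 44). Under Section 3.2.3 only a day-30 visit is. FU1 lung tests can fall on either side of the limit, so literal application would select data by booking date. Separately, non-fatal AEs and SAEs on days 31–90 from Core completers not entering the extension have no planned summary. It would be too strong to say that late safety data are lost, since they are collected and listed and fatal events are summarised.

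The day ranges assume that visits keep to their stated windows and that the lung-test allowance in Section 7.3.3 applies to FU1, as its wording for all remaining visits implies. The number of subjects affected cannot be derived from the documents. The endpoints are descriptive and the primary PD analysis is untouched, so this is a minor point.

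**What to change.** 1. In Sections 11.2.2 and 11.2.10, limit the 30-day cut to counts of treatment-emergent events and abnormalities, in line with Section 6.2.
2. In the same places, state that scheduled FU1 and FU3 assessments and the reversibility endpoints are analysed by visit regardless of the cut.
3. Reconcile the FU1 and FU2 anchor between Table 1 (EOT1) and Section 3.2.3 (last dose), and the EOT1 timing between Sections 3.2.2 and 8.2.6. The AE collection period needs the same check: note 7 of Table 1 counts from EOT1, and Section 10.1.5 counts from treatment discontinuation.
4. Add one descriptive table of AEs and SAEs with onset from day 31 to FU2, labelled post-treatment, with a note that later standard of care may confound these events.

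The cost is wording plus one table. No new data are needed.
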